## **Project Description**

The studies will be conducted using our well-established techniques and methods. Exposure to controlled levels of motor exhaust from diesel fuel has been conducted for more than two decades, and in recent years we have also developed a collaboration with Associate [name] group at the Thermochemical Energy Conversion Laboratory (TEC-Lab) at Umeå University. This offers a unique opportunity to study under different combustion conditions.

**Hypothesis:** Diesel exhaust cause cell dysfunction in the olfactory system secondary to mitochondrial dysfunction and oxidative stress. Additionally, we hypothesize that these exposures result in measurable effects on the sense of smell and cognitive ability.

## **Project Description**

The studies will be conducted using our well-established techniques and methods. Exposure to controlled levels of diesel fuel exhaust has been studied for over two decades.

**Hypothesis:**

Diesel exhaust gases cause cell dysfunction in the olfactory system secondary to mitochondrial dysfunction and oxidative stress. The hypothesis also includes studying whether exposures lead to measurable effects on the sense of smell and cognitive abilities.

## **Study Design**

Forty people will be exposed to diesel exhaust gases and filtered air. Exposures will be blinded and randomized. Both groups will undergo mucosal biopsies of the olfactory epithelium after local anesthesia following exposure.

All samples collected during the study will be coded, and data will be processed in a blinded manner.

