#### **Specific aim:**

- To study the oxidative and inflammatory effects of exposure to diesel exhaust on the respiratory epithelium and the olfactory nerve in healthy individuals. Additionally, the study aims to determine whether these exposures result in measurable effects on the sense of smell and cognitive ability.

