### Olfactory Epithelium Biopsy

After local anesthesia with Xylocain following exposure, a small biopsy of the nasal mucosa will be taken by a specialist doctor. Material from the nasal biopsies will be used both for culture experiments and for later analyses, including PCR analysis after freezing at -80°C, and will be sent to our collaborators, [name] and [name] at the University of Eastern Finland. Nasal mucosa biopsies have been performed previously at the ENT department at Umeå University following ethical approval. Complication risks are virtually nonexistent, but there may be minor discomfort or slight nasal bleeding, which can be easily stopped using a compress applied to the biopsy site. ENT doctors are experienced in managing nasal bleeding. Biopsy sampling will be randomized between the left and right sides across two exposure sessions, with the contralateral biopsy taken after the second exposure.

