### Olfactory Testing

The Sniffin' Sticks test (Hummel et al., 1997), a commercially available test, will be used to determine the participant's odor detection threshold. The odorant (n-butanol) is presented in marker pens filled either with n-butanol or a blank (no odor). The test uses 16 concentrations of n-butanol, from the weakest concentration (1.2 ppm n-butanol) to the strongest (4% n-butanol). In a "triple-forced-choice paradigm," the detection threshold is determined using a staircase method (Doty, 1991). Three pens are presented in a randomized order—two with blank stimuli and one with the odorant at a given concentration. The participant's task is to identify which pen contains the odorant.

Participants wear eye masks to prevent visual identification of the pens. The pen is placed approximately 2 cm below the nostrils for about 3 seconds. The test starts at the 8th concentration level, and if the participant correctly identifies the odorant four times in a row,

the test continues with higher concentrations. If the participant fails to do so, the test proceeds to lower concentrations.

The test has good test-retest reliability (Albrecht et al., 2008) and validity (Ribeiro et al., 2016). The exposure levels of n-butanol are much lower than the occupational exposure limit of 15 ppm (45 mg/m^3), so no toxic effects or discomfort risks are expected.

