### Cognitive Testing

Cognitive ability will be assessed using the Letter Digit Substitution Test, a paper-and-pencil test that evaluates working memory, processing speed, and attention. A key at the top of the page provides the correct mapping for the numbers 1 to 9, which are paired with specific letters. Below the key, there are 120 letters (9 different ones), each connected to a blank square. The participant's task is to write as many numbers as possible in the empty squares under a 60-second time limit according to the letter-number mapping provided in the key.

The test has good test-retest reliability (Hoex et al., 2002) and validity (Natu & Agarwal, 1995). There is no risk of pain or discomfort associated with the test.

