### Blood Tests

Blood samples will be taken before exposure and before olfactory epithelium biopsies. These will be analyzed for cell count, inflammation markers, and lymphocyte subtyping using flow cytometry. A maximum of 100 ml of blood will be drawn during each exposure.

The effects of exposure to air pollution at the cellular level will be studied in monocytes from peripheral blood using in-vitro tests. Further analyses, including PCR (polymerase chain reaction), will be conducted for the APOE gene, a genetic factor that can influence sensitivity to air pollution. These analyses will be performed at Kuopio University, Finland.

RNA sequencing and DNA methylation will also be conducted to identify biomarkers for acute exposure to air pollution at the Institute of Experimental Medicine, Czech Academy of Science, Czech Republic.

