### COVID-19 Testing

Participants will be tested for SARS-CoV-2 before each exposure session.

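### Do the undefined groups in the Study Design section, and the unstated timing of the smell and cognitive tests, leave the design open?

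*Protocol*

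**What the plan says.** The Study Design section of the Protocol opens with "Forty people will be exposed to diesel exhaust gases and filtered air. Exposures will be blinded and randomized". It then says "Both groups will undergo mucosal biopsies of the olfactory epithelium after local anesthesia following exposure". No section defines groups, uses the word crossover or parallel, or gives the interval between sessions.

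Other sections describe the visits. Olfactory Epithelium Biopsy says "Biopsy sampling will be randomized between the left and right sides across two exposure sessions, with the contralateral biopsy taken after the second exposure". COVID-19 Testing says "Participants will be tested for SARS-CoV-2 before each exposure session". Blood Tests caps the blood volume per exposure and fixes the sampling times: "Blood samples will be taken before exposure and before olfactory epithelium biopsies".

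Smell and cognition belong to the Specific aim: "the study aims to determine whether these exposures result in measurable effects on the sense of smell and cognitive ability". Olfactory Testing describes the test that "will be used to determine the participant's odor detection threshold", and Cognitive Testing says "Cognitive ability will be assessed using the Letter Digit Substitution Test". Both sections describe how the test is run. Neither says at which sessions it is done, or whether it comes before or after exposure, Xylocain or biopsy.

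**The concern.** Two separate points arise.

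- **Design.** The section that should fix the design uses a word that suggests parallel arms, while the biopsy section implies two sessions per person. The reading decides what is randomised (arm or order), whether comparisons are within or between people, and how many biopsies are taken: 2 × 40 = 80 with two sessions each, 40 with one. It also decides how much 40 participants can show. A related worry is that biopsy side is randomised with no stated link to exposure order, so side and exposure could be unbalanced by chance.
- **Test timing.** An odour threshold measured after nasal anaesthetic and removal of olfactory tissue may reflect those rather than diesel exhaust. Because blood sampling is given a place in the sequence, its absence for two outcomes named in the aim stands out. An analysis plan cannot repair measurements taken in the wrong order.

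**Working it through.** **1. Which design does the text describe?** The Protocol gives no significance level, power, effect size or SD, so there is no sample-size figure to reproduce. The relevant statements are these:

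| Section | Statement | Points to |
|---|---|---|
| Study Design, first sentence | Forty people receive diesel exhaust and filtered air | Both exposures per person |
| Olfactory Epithelium Biopsy | Two sessions, opposite side sampled after the second | Both exposures per person |
| Blood Tests | Volume limit applies to each exposure | More than one exposure |
| COVID-19 Testing | Test before each session | More than one session |
| Study Design, third sentence | Groups, undefined | Parallel arms, or two order groups |

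No section says that anyone receives a single exposure. If everyone receives both and the exposures are randomised, order is the only exposure allocation left to randomise. Under the order-group reading the odd word does not conflict with anything.

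**2. What would a parallel reading cost?** Assumptions, none from the Protocol: two-sided 5%, 80% power, within-person correlation r = 0.3, 0.5 or 0.7. By the noncentral t distribution, 40 pairs detect 0.454 SD of the paired difference. In units of the outcome SD the same effect is 0.454 × √(2(1 − r)):

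| r | Effect (outcome SD) | Power, 20 per group | Total for 80% power, parallel |
|---|---|---|---|
| 0.3 | 0.537 | 38% | 112 |
| 0.5 | 0.454 | 29% | 156 |
| 0.7 | 0.352 | 19% | 256 |

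The contrast is large, but it only shows that crossovers are more efficient than parallel trials. It is no loss in this trial, because step 1 finds no support for a parallel design.

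**3. Biopsy side and exposure order.** Suppose the two are randomised separately, which the Protocol does not state. A diesel-by-side split of 24/16 or worse then occurs:

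- with simple randomisation, Binomial(40, 0.5): probability 0.268;
- with two separate 20/20 lists, diesel-on-left count 2X with X hypergeometric (40, 20, 20): probability 0.343.

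At 24/16 an unadjusted contrast takes up (24 − 16)/40 = 0.20 of any left-right difference. This is chance imbalance. Averaged over randomisations it is zero, so the contrast is unbiased. With side in the model, the information kept at 24/16 is 1 − 0.20² = 0.96, equal to 40 × 0.96 = 38.4 participants. A simulation of 20,000 replicates, with a left-right difference of 0.5 SD of the paired difference and side modelled, gave power 0.791 (simple), 0.785 (two lists) and 0.796 (one joint list of four sequences of 10). The gain is about one percentage point.

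**4. Test timing.** Let D and F be a person's results after diesel and filtered air.

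- If anaesthetic and biopsy shift both results by the same amount a, then (D + a) − (F + a) = D − F, and the contrast is unchanged.
- If they shrink both results by a factor k below 1, the contrast becomes k(D − F), which is smaller but not spurious.

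A fixed order at both sessions, even a poor one, would therefore mainly mask an effect. A smell test at the second session also follows the first session's biopsy. That is a period effect, removed by balanced order or by period adjustment unless it depends on which exposure came first. The size of any masking cannot be computed from the Protocol.

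**The case for a change.** The strongest case for a change rests on test timing. Smell and cognition are in the aim and the hypothesis, the sequence is a protocol matter, and the authors did place blood sampling. Nothing in the text prevents an odour test after Xylocain, or an order that differs between sessions, which would add noise or bias. A sentence would settle it at almost no cost.

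The gap is real, and that much stands. But the Protocol states no wrong order; the harmful sequence is a scenario that the text merely fails to exclude. A team running a controlled exposure study with ENT specialists can be expected to test smell before numbing the nose, and to do the same at both sessions. Fixing the order also has a price: the smell test is a 16-level staircase with three pens per presentation and no stated duration, and the biopsy would wait for it.

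On the design, it is fair that the section bearing that name should name it. But correcting the word would alter no visit, biopsy, allocation or comparison. The structure of the randomisation list and the factors in the model are commonly left to a randomisation plan or SAP, which is not shown here.

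**Conclusion.** No change to the plan follows. The reference to groups is a loose phrase in a protocol that otherwise describes one within-person, two-session design; tidying it would be clerical. The missing test timing is a detail that investigators would fill sensibly. It has no computable size, and under a fixed order it would mainly weaken a true difference. A joint list for side and order is optional, worth about one percentage point of power under the simulated left-right difference.

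This rests on three assumptions: that everyone attends both sessions, as all the session-level statements imply; that the tests keep the same place in the sequence at both sessions; and that smell is tested before the anaesthetic, as ordinary practice would suggest. Evidence that participants receive only one exposure, or that test order differs between diesel and filtered-air sessions, would reopen the point.

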**ResearchParticipants:**

Forty healthy, non-smoking individuals aged 20-70 years will be included. Strict inclusion and exclusion criteria will be applied based on a medical assessment as outlined above.

## **Exposure to Diesel Exhaust**

Diesel exhaust will be generated using a Volvo diesel engine. More than 90% of the exhaust will be shunted, with the remaining portion mixed with filtered air (HEPA filter) and directed into the exposure chamber at a concentration of 300  $\mu\text{g}/\text{m}^3$  using techniques established over decades. The exposure will last for 1 hour, blinded and randomized. During the exposure, participants will alternate between 15-minute periods of rest and exercise on an ergometer cycle with a load that ensures a minute ventilation of 20L/min/m^2 body surface area. Symptoms will be recorded every 30 minutes based on a modified Borg scale.

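### Does calling the exposures blinded, without saying for whom or how, and with no exposure guess described, need a change to the plan?

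*Protocol*

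**What the plan says.** Two sections of the protocol assert blinding. Study Design states "Exposures will be blinded and randomized", and Exposure to Diesel Exhaust states "The exposure will last for 1 hour, blinded and randomized". Neither names the participant, the chamber staff, the tester or the biopsy doctor as blind, and neither describes a method.

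One concrete step is given, also in Study Design: "All samples collected during the study will be coded, and data will be processed in a blinded manner".

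The outcomes that depend on the participant are described in three places:

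- **Symptoms** (Exposure to Diesel Exhaust): "Symptoms will be recorded every 30 minutes based on a modified Borg scale". The rater is not named.
- **Smell threshold** (Olfactory Testing): three pens in random order, one holding the odorant. "Participants wear eye masks to prevent visual identification of the pens".
- **Cognition** (Cognitive Testing): the participant must "write as many numbers as possible in the empty squares under a 60-second time limit".

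The hypothesis under Project Description covers the last two: "we hypothesize that these exposures result in measurable effects on the sense of smell and cognitive ability". Olfactory Epithelium Biopsy indicates that each participant attends twice: "Biopsy sampling will be randomized between the left and right sides across two exposure sessions, with the contralateral biopsy taken after the second exposure".

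**The concern.** Diluted diesel exhaust and filtered air may well smell different, and two sessions let a participant compare one with the other. No sham or odour masking is described. The eye masks hide the pens, not the exposure.

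A participant who recognises the diesel session might report more symptoms, or try less hard on a 60-second speed test. A difference between exposures could then partly reflect expectation. The report might describe participants as blinded with nothing in the protocol to support it. A guess that was never requested cannot be recovered later, so this would have to be settled before the sessions run. Who is blinded is also ordinary protocol content, so the gap cannot simply be assigned to an unseen SAP.

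**Working it through.** **1. What the text supports.** The protocol gives no power calculation and no figure on detectability, so there is no planned figure to reproduce. Setting the sections side by side:

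| Outcome | Protection described | In aim or hypothesis | Room for expectation bias |
|---|---|---|---|
| Biopsy, RNA, methylation, blood | Coded samples, blinded processing | Yes, as cellular effects | Little |
| Smell threshold | Forced choice, random pen order, eye masks | Yes | Small, through attention |
| Letter Digit Substitution Test | None during the session | Yes | Some, through effort |
| Borg symptoms | None; rater not named | No | Most, if self-rated |

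The outcome most open to bias is the least central one. Recognition itself is an inference. The protocol says only that more than 90% of the exhaust is shunted and that the rest is mixed with filtered air to reach 300 µg/m³.

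**2. How large the bias could be, under assumptions.** The protocol gives 40 participants. Reading the two sessions as a crossover gives 40 pairs. Two inputs are assumed: a share r recognises diesel, and recognition shifts their score by b SD of the within-person difference. There is no true effect. The standardised mean difference is then

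d = r·b / √(1 + r(1 − r)b²),

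and the paired t statistic on 39 degrees of freedom has noncentrality d·√40. For b = 0.2 and r = 0.25, d = 0.05 / √(1 + 0.1875 × 0.04) = 0.0498 and the noncentrality is 0.315.

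Two-sided rejection rates at the 5% level:

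| Shift b | r = 25% | r = 50% | r = 100% |
|---|---|---|---|
| 0.1 SD | 5.3% | 6.1% | 9.5% |
| 0.2 SD | 6.1% | 9.4% | 23.5% |
| 0.3 SD | 7.5% | 15.0% | 45.7% |

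These rates count significant results in both directions, and the rate with no unblinding is already 5% (2.5% each way). At b = 0.2 and r = 25%, the 6.1% consists of 4.9% in the direction of the shift and 1.2% the other way. The excess over 5% is therefore about 1 percentage point. The two largest entries require every participant to recognise diesel.

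**3. What a guess question would show.** With 40 answers from session 1, the two-sided binomial test against 50% is significant from 27 correct (p = 0.038; 26 correct gives p = 0.081). If non-recognisers guess at random, P(correct) = 0.5 + r/2.

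- r = 25%: P = 0.625, power 32%.
- r = 50%: P = 0.75, power 90%.
- 27 of 40 correct: 67.5%, exact 95% CI 51% to 81%.
- 20 of 40 correct: exact 95% CI 34% to 66%.

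A result at chance would not establish that the blind held, and one above chance could come from genuine symptoms as well as from odour.

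**The case for a change.** The strongest case for a change is that the protocol asserts blinding twice without support, that blinding belongs in a protocol, and that the remedy is cheap: a sentence naming the blinded parties and one short question after the tests in each session. The question does not require recognition to be true; it would measure it. Smell and cognition are stated aims and both are measured on the participant's own performance.

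Part of this stands. The description is incomplete, and a sentence saying who is blind and how would improve it. If participant blinding cannot be supported, the report should not claim it. The step from there to a defect in the plan does not hold. The guess question measures unblinding without removing it and is confounded by real effects of the exposure. It also could not properly be used to downgrade a result, so no analysis or conclusion turns on it. Statisticians differ on whether such questions are worth asking, and leaving one out is a defensible choice.

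The time of the smell test relative to exposure is a separate matter. It does not bear on who is blinded, and nothing in the protocol indicates that a short-lived shift would be an artefact in a study that looks for acute effects.

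**Conclusion.** No change to the plan is called for. The blinding statement is under-described, but no passage contradicts it or shows it to be untrue. The laboratory outcomes have stated protection, the smell test limits response bias by its design, and the symptom scale is outside the aim and hypothesis. That leaves mainly the timed cognitive test, where the effect would act indirectly through effort.

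On the assumed figures, the excess over the nominal 5% is about 0.3 to 2.5 percentage points if a quarter recognise diesel. It becomes large only if recognition is near universal and the shift is 0.2 SD or more. These sizes rest on assumed recognition shares and shifts and on reading the design as a crossover; none of them is evidence that bias will occur. Stating who is blind and how is a clarification that the investigators can make when they write up the study. An exposure guess would be optional and descriptive only.

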### Olfactory Epithelium Biopsy

After local anesthesia with Xylocain following exposure, a small biopsy of the nasal mucosa will be taken by a specialist doctor. Material from the nasal biopsies will be used both for culture experiments and for later analyses, including PCR analysis after freezing at -80°C, and will be sent to our collaborators, [name] and [name] at the University of Eastern Finland. Nasal mucosa biopsies have been performed previously at the ENT department at Umeå University following ethical approval. Complication risks are virtually nonexistent, but there may be minor discomfort or slight nasal bleeding, which can be easily stopped using a compress applied to the biopsy site. ENT doctors are experienced in managing nasal bleeding. Biopsy sampling will be randomized between the left and right sides across two exposure sessions, with the contralateral biopsy taken after the second exposure.

### In-Vitro Studies and Biomarker Analysis

Effects at the cellular level of exposure to air pollution will be studied in olfactory epithelial cells using in-vitro tests at the University of Kuopio, Finland. RNA sequencing and DNA methylation will be conducted to identify biomarkers for acute exposure to air pollutants at the Institute of Experimental Medicine, Czech Academy of Science, Czech Republic.

### Olfactory Testing

The Sniffin' Sticks test (Hummel et al., 1997), a commercially available test, will be used to determine the participant's odor detection threshold. The odorant (n-butanol) is presented in marker pens filled either with n-butanol or a blank (no odor). The test uses 16 concentrations of n-butanol, from the weakest concentration (1.2 ppm n-butanol) to the strongest (4% n-butanol). In a "triple-forced-choice paradigm," the detection threshold is determined using a staircase method (Doty, 1991). Three pens are presented in a randomized order—two with blank stimuli and one with the odorant at a given concentration. The participant's task is to identify which pen contains the odorant.

Participants wear eye masks to prevent visual identification of the pens. The pen is placed approximately 2 cm below the nostrils for about 3 seconds. The test starts at the 8th concentration level, and if the participant correctly identifies the odorant four times in a row,

the test continues with higher concentrations. If the participant fails to do so, the test proceeds to lower concentrations.

The test has good test-retest reliability (Albrecht et al., 2008) and validity (Ribeiro et al., 2016). The exposure levels of n-butanol are much lower than the occupational exposure limit of 15 ppm (45 mg/m^3), so no toxic effects or discomfort risks are expected.

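### Do the smell and cognitive tests need a stated time point and a same-session pre-exposure value?

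*Protocol*

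**What the plan says.** The Specific aim section makes both outcomes part of the study's purpose: "Additionally, the study aims to determine whether these exposures result in measurable effects on the sense of smell and cognitive ability". The hypothesis repeats this.

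The Olfactory Testing section covers the pens, the sixteen concentrations, the staircase, the eye mask and the presentation ("The pen is placed approximately 2 cm below the nostrils for about 3 seconds"). The Cognitive Testing section names the instrument ("Cognitive ability will be assessed using the Letter Digit Substitution Test, a paper-and-pencil test that evaluates working memory, processing speed, and attention") and its 60-second limit, which is the length of the test and not its place in the session. Neither section says when the test is given relative to exposure, anaesthetic or biopsy, how often, or whether a pre-exposure value is taken.

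Other session procedures are timed:

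- Symptoms: "Symptoms will be recorded every 30 minutes based on a modified Borg scale".
- Biopsy: "After local anesthesia with Xylocain following exposure, a small biopsy of the nasal mucosa will be taken by a specialist doctor".
- Blood (Blood Tests section): drawn ahead of exposure and again ahead of the biopsy.
- SARS-CoV-2 (COVID-19 Testing section): tested ahead of every session.

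On the design, Study Design states "Forty people will be exposed to diesel exhaust gases and filtered air", and the biopsy section adds "Biopsy sampling will be randomized between the left and right sides across two exposure sessions, with the contralateral biopsy taken after the second exposure". Study Design also contains the sentence "Both groups will undergo mucosal biopsies of the olfactory epithelium after local anesthesia following exposure".

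**The concern.** Four things make this look like a defect.

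1. Two outcomes named in the aim are untimed in a short protocol that times most other session procedures. The gap therefore does not look like general brevity.
2. The session includes local anaesthesia and biopsy of the nasal mucosa. If odour threshold were measured afterwards in both sessions, an effect of diesel could be masked. If the order varied between sessions, noise or bias could enter.
3. A pre-exposure value that was never collected cannot be supplied later by an analysis plan.
4. One side of the nose has already been biopsied by the second session, and the pen is held below both nostrils. The interval between sessions is not given, so any lasting effect cannot be judged.

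The reference to two groups in Study Design adds doubt. If the design were parallel, there would be no within-person control and a baseline would matter more. The anaesthetic and biopsy bear on smell only; for cognition the issue is the missing time point and baseline.

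**Working it through.** **Timing, from the text.** The anaesthetic and biopsy come after exposure. The smell test is not ordered against them. Two placements fit the text: after the anaesthetic, or between exposure and anaesthetic, where the second blood sample already sits. The text favours neither, and no section states that the anaesthetic changes odour threshold. No stated rule is wrong.

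**Design, from the text.** Study Design has forty people exposed to diesel exhaust and filtered air. The biopsy section has two sessions per person, with the opposite side sampled after the second. Only a crossover fits both. The reference to groups is a wording slip that the biopsy section resolves.

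**Value of a baseline.** The protocol gives no power, alpha, effect size or SD, so there is no figure of its own to reproduce. Assumptions: n = 40 in two sessions, two-sided alpha 0.05, and 80% power from post-exposure values alone. Work in SDs of the within-person diesel-minus-air difference, and let ρ be the correlation between the pre-exposure and post-exposure session differences.

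- Starting point: a paired t-test with 39 df has 80% power at a standardised difference of 0.454. With a period term (38 df) power is 79.9%.
- Baseline as covariate: the residual variance is 1 − ρ², with 37 df.
- Baseline subtracted: the variance is 2(1 − ρ), with 38 df.

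| ρ | 1 − ρ² | Adjusted, closed form | Adjusted, simulated | 2(1 − ρ) | Subtracted, closed form |
|---|---|---|---|---|---|
| 0 | 1.000 | 79.9% | about 79% | 2.0 | 50.8% |
| 0.25 | 0.938 | 82.4% | about 81% | 1.5 | 62.8% |
| 0.5 | 0.750 | 89.8% | about 89% | 1.0 | 79.9% |

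The simulation (60,000 runs; difference modelled on period and pre-exposure difference) is the better guide. The closed form ignores the cost of estimating the covariate slope when the baseline differences are not exactly centred. Against the 80% start, the gain is 79 − 80 = −1 point at ρ = 0 and 89 − 80 = +9 points at ρ = 0.5. Subtracting the baseline does not help at any of the three correlations.

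**Earlier biopsy.** Assume a person-to-person shift with SD 0.5 in the same units and ρ = 0.

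- Post-exposure values only: variance 1 + 0.5² = 1.25, power 70.7%.
- Adjusted: the shift is shared by the pre and post differences of a session, so the variance is 1.25 − 0.25²/1.25 = 1.20, power 72.4% (71.4% by simulation).

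A baseline therefore does almost nothing about this. With randomised order the shift is mainly a period effect, and the documents report only minor discomfort or slight bleeding after biopsy.

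**The case for a change.** The strongest opposing case is that assessment timing is study conduct and cannot be left to an analysis plan. Intent that is not written down does not bind staff, the omission affects outcomes in the aim, and the remedy costs one or two sentences. All of this is fair. The textual gap is real, and an absent SAP does not excuse it. Writing the time points down would be good housekeeping.

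What does not stand is the step from a gap to a flaw. The harmful reading needs the team to test smell through an anaesthetised nose, which the protocol does not plan. If that happened in both sessions it would apply under both exposures, so the likely result would be a blunted effect; bias would need the order to differ between sessions.

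The parallel-group reading would raise the stakes. With 20 per group, the detectable difference at 80% power would be (1.960 + 0.842) × √(2/20) = 0.89 between-person SDs, and a baseline would be more useful. That reading does not survive the biopsy section's two sessions per person.

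The irreversibility argument holds for the baseline, but what would be lost is precision of uncertain size. Extra administrations also lengthen the session and may add practice on the cognitive form.

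**Conclusion.** The observation is accurate, but it does not call for a change to the plan. The missing time points are a gap that investigators fill sensibly, with a natural slot at the blood draw before biopsy. The absent baseline is a fair trade-off: under the two-session design the randomised diesel-air comparison is valid without it. Its worth runs from about −1 to +9 power points for correlations of 0 to 0.5, against a longer session and possible practice effects. Carry-over from the first biopsy is noise rather than bias, and a baseline would move power by only one or two points under the shift assumed. The reference to two groups is a wording slip. Period terms and covariate adjustment are matters commonly left to an SAP, which is not shown here.

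The conclusion rests on reading the design as two randomised sessions per person. The figures rest on the assumed 80% starting power, correlations and biopsy shift, none of which the protocol supplies. No figure is offered for the anaesthetic, because the protocol fixes no order and states no effect of it on threshold.
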